8.2.3.1.3 Exploratory Endpoints

Best Overall Response per RECIST 1.1 [Appendix 12.4]: the best response attained during the study with 4 categories based upon RECIST 1.1 by the investigator review: Complete Response (CR), Partial Response (PR), Stable Disease (SD), and Progressive Disease (PD). Categories of CR and PR need to be confirmed in this endpoint.

5-Category Best Overall Response (BOR-5) – an ordinal endpoint that represents the best response attained during the study with 5 categories: CR (confirmed), Very Good Partial Response (VGPR) defined as confirmed partial response with maximum percent reduction

from baseline in tumor line length >60%, Moderate Partial Response (MPR) defined as confirmed partial response with maximum percent reduction from baseline in tumor line length \leq 60%, SD, and PD. In this endpoint, CR, PR, SD and PD categories are based upon RECIST 1.1 by the investigator review and the RECIST 1.1 category of PR is split into two categories: VGPR and MPR.

5-Category Ordinal Response at a Timepoint – an ordinal endpoint that classifies the response at given timepoint into one of 5 categories: CR, VGPR defined as partial response with percent reduction from baseline in tumor line length >60%, MPR defined as partial response with percent reduction from baseline in tumor line length \leq 60%, SD, and PD. In this endpoint, CR, PR, SD and PD categories are based upon RECIST 1.1 by the investigator review. No confirmation will be required for complete or partial responses at a timepoint. Subjects who discontinued prior to timepoint will be assigned to one of these categories according to their reason for discontinuation. Subjects who discontinued for the following reasons will be included in the PD category: documented disease progression, unacceptable adverse event(s), intercurrent illness that prevents further administration of treatment, noncompliance with trial treatment or procedure requirements, investigator’s decision to withdraw the subject, subject withdraws consent. Subjects who discontinued due to pregnancy of the subject or for administrative reasons will be included in the SD category. Subjects who attained an investigator-determined confirmed complete response (CR) per RECIST 1.1 and stopped the trial treatment will be included in the CR category. The categories are assigned scores 1 to 5 for analysis: CR=1, VGPR=2, MPR=3, SD=4, PD=5.

Percentage of Subjects with CR based upon RECIST 1.1 by the investigator review

Percentage of Subjects with PR based upon RECIST 1.1 by the investigator review

Percentage of Subjects with Deep Response (DR) where DR is a response that is either CR or VGPR by the investigator review.

Best Target Lesion Response - maximum percent reduction in tumor line length over target lesions by the investigator review.

Time to Confirmed Response – defined only for subjects with confirmed response by the investigator review. The time interval between the date of randomization and the date of the first confirmed response (CR/PR) (the response prior to confirmation).

Percentage of Subjects with Sustained Response at Week 36 (used in the interim analysis) - subjects who achieved response (confirmed CR or PR) prior to Week 36 but have not yet progressed at Week 36 by central review.

Tumor growth kinetics endpoints: growth rate constant (GST) and time-to-growth (TTG) and other as appropriate. These endpoints will be used in Modeling and Simulations analysis.

EuroQol (EQ-5D) and EORTC (QLQ-C30) endpoints

Additional supportive analyses of PFS, objective response rate, best overall response, and duration of response will be conducted using modified RECIST 1.1 criteria, in which a confirmation assessment of disease progression must be obtained at least 4 weeks after the initial disease assessment indicating progressive disease.

8.2.3.2 Safety Endpoints

The primary safety endpoint in Parts 1, 2, 4, and 5 of the study is DLT. In Part 3, there will be no Tier 1 safety endpoints; Tier 2 and Tier 3 safety endpoints will be evaluated as described in 8.2.5.4. Safety will be monitored by cumulative data reviews throughout the trial. The toxicities and grades experienced by subjects who have received study treatment, including adverse events (AEs), serious adverse events (SAEs) and events of clinical interest (ECIs) will be summarized. Other safety measures evaluated in all parts of the study include laboratory safety assessments, ECGs, vital signs, and physical examinations.

8.2.4 Analysis Populations

8.2.4.1 Efficacy Analysis Populations

The primary analysis population in Part 3, Intent-to-Treat Analysis Set (ITT), will include all randomized subjects. The ITT will serve as the primary population for the analyses of PFS, OS, and ORR in this study. Analysis of response duration is based on all confirmed responders.

In Parts 1, 2, 4, and 5 of the study the All-Subjects-as-Treated (ASaT) will be used for efficacy analyses. Analysis of response duration will be based on all confirmed responders in the ASaT.

8.2.4.2 Safety Analysis Populations

The ASaT population will be used for the analysis of safety data in this study. In all parts of the study, the ASaT population consists of all subjects who received at least one dose of study treatment. In Parts 4 and 5, subjects treated during the trametinib run-in period will be included in the ASaT population even if they discontinued treatment before receiving pembrolizumab. In case of treatment administration errors, subjects will be analyzed according to the treatment they actually received.

At least one laboratory or vital sign measurement obtained subsequent to at least one dose of study treatment is required for inclusion in the analysis of each specific parameter. To assess change from baseline, a baseline measurement is also required.

The DLT analysis will be performed on a DLT-evaluable population.

In Parts 1 and 2, a DLT evaluable subject is defined as a subject who receives at least 66% of all planned treatments during the 6-week DLT observation period (i.e., Cycle 1, initiated with

the first pembrolizumab dose) or a subject who discontinues the DLT observation period due to a DLT. In Parts 4 and 5, a DLT evaluable subject is defined as a subject who receives at least 66% of all planned treatments during the 6-week DLT observation period (i.e., following the trametinib run-in period in Cycle 1, initiated with the first pembrolizumab dose) or a subject who discontinues the DLT observation period due to a DLT. In Parts 4 and 5, any subject who discontinues trametinib during the trametinib monotherapy run-in period is not considered evaluable for DLTs for the (MK+T) combination, even if the subject discontinued due to a DLT.

8.2.5 Statistical Methods

8.2.5.1 Statistical Methods for Efficacy Analyses

Parts 1, 2, 4 and 5 in Subjects Treated with (MK+D+T) or (MK+T)

The best overall response and PFS based on the investigator review per RECIST 1.1 in subjects along with baseline characteristics will be listed. Percentage of subjects that attained Objective Response will be estimated.

Part 3

The analysis strategy for primary and secondary endpoints in Part 3 is summarized in [Table 40](#).

Table 40 Analysis Strategy for Primary and Secondary Efficacy Endpoints in Part 3

Endpoint (Description, Time Point)	Approach [†]	Statistical Method [‡]	Analysis Population	Missing Data Approach
Progression-free-survival	P	Testing: Stratified Log-rank test Estimation: Stratified Cox model with Efron's tie handling method Kaplan-Meier method for PFS curve estimation in each treatment group	ITT	Censored at last assessment
Objective response rate	S	Stratified Miettinen and Nurminen method [100]	ITT	Subjects with missing data are considered as non-responders
Response Duration	S	Summary statistics using Kaplan-Meier method	All responders	Non-responders are excluded in analysis
Overall survival	S	Summary statistics using Kaplan-Meier method	ITT	Censored at last date
[†] P=Primary , S=Secondary				

Primary endpoint in Part 3 is PFS. The treatment groups will be compared in PFS by stratified log-rank test. While the randomization is stratified by ECOG PS (0 vs. 1) and LDH (>1.1xULN vs. ≤1.1xULN), due to a very low number of subjects enrolled in the stratum ECOG=1 and LDH ≤1.1xULN, the two strata with ECOG=1 (ECOG=1 and LDH ≤1.1xULN; ECOG=1 and LDH >1.1xULN) will be combined for all analyses. A Cox proportional hazard model with a factor for treatment group stratified using the strata above with Efron's method of tie handling will be used to estimate the hazard ratio and its 95% confidence interval. The Kaplan-Meier method will be used to estimate the PFS survival curve, the median PFS and its 95% CI, PFS at 44 weeks (10.1 months) and its 95% CI, and PFS at 74 weeks (17 months) and its 95% CI will be estimated. The time points chosen for estimation are close to the expected time of median PFS in the (PBO+D+T) treatment group (44 weeks) and the respective smallest detectable median in the (MK+D+T) treatment group. Both time points are placed 2 weeks after the scheduled visit as lower variability of the Kaplan-Meier estimate is expected outside of the clinic visit window.

For PFS, subjects without documented PD/death will be censored at the last disease assessment date or, if they started new anti-cancer treatment, at the last disease assessment before initiation of the new anticancer treatment (Table 40). Two sensitivity analyses of PFS will be performed. The rules for defining the time of progression or censoring in the primary and two sensitivity PFS analyses are provided in Table 41.

Table 41 Censoring Rules for Primary and Sensitivity Analyses of PFS

Situation	Primary Analysis	Sensitivity Analysis 1	Sensitivity Analysis 2
No PD and no death; new anticancer treatment is not initiated	Censored at last disease assessment	Censored at last disease assessment	Censored at last disease assessment if still on study therapy; progressed at treatment discontinuation otherwise
No PD and no death; new anticancer treatment is initiated	Censored at last disease assessment before new anticancer treatment	Censored at last disease assessment before new anticancer treatment	Progressed at date of new anticancer treatment
PD or death documented after ≤ 1 missed disease assessment	Progressed at date of documented PD or death	Progressed at date of documented PD or death	Progressed at date of documented PD or death
PD or death documented after ≥ 2 missed disease assessments	Progressed at date of documented PD or death	Censored at last disease assessment prior to the ≥ 2 missed disease assessment	Progressed at date of documented PD or death

ORR will be estimated as the percentage of responders among subjects in each treatment group. 95% CIs for within-group ORRs will be provided using the Clopper-Pearson method [102]. The treatment comparison between arms will be based on Miettinen and Nurminen's method [100] based on difference in proportions stratified using strata from the PFS analysis.

The response duration analysis will include subjects who achieved objective response. The responders who have not yet progressed by the last disease assessment will be censored at the last disease assessment date. The treatment groups will be compared in response duration by log-rank test stratified using strata from the PFS analysis. A Cox proportional hazard model with a factor for treatment group stratified using the strata from the PFS analysis with Efron's method of tie handling will be used to estimate the hazard ratio and its 95% confidence interval. The Kaplan-Meier method will be used to estimate the response duration survival curve, the 25-th percentile and the median of response duration and their 95% CIs.

Time to response analysis will include all subjects who achieved objective response, and thus, will contain no censored endpoints. The Kaplan-Meier method will be used to estimate the time to response survival curve, the 25th percentile and the median of response duration and their 95% CIs.

The treatment groups will be compared in OS by log-rank test stratified using the strata from the PFS analysis. A Cox proportional hazard model with a factor for treatment group stratified by the covariates above with Efron's method of tie handling will be used to estimate the hazard ratio and its 95% confidence interval. The Kaplan-Meier method will be used to estimate the OS survival curve, the 25th percentile and the median of OS and their 95% CIs. Subjects without documented death at the time of analysis will be censored at the date last known to be alive.

Best Overall Response (BOR) will be summarized by treatment groups, with frequency of categories presented. BOR-5 will be analyzed by ANOVA on scores 1 to 5 assigned to the response categories: CR=1, VGPR=2, MPR=3, SD=4, PD=5. ANOVA will include factors for treatment group, ECOG PS (0 vs. 1) and LDH (>1.1xULN vs. ≤1.1xULN). The variances in the two treatment groups will be allowed to be unequal. The desired effect of the addition of pembrolizumab to the (PBO+D+T) combination is to shift BOR response towards lower scores, [lower the treatment group mean score of (MK+D+T) compared to (PBO+D+T)].

Individual Best Target Lesion Responses (maximum percent reduction in tumor line length over target lesions) will be plotted for each treatment group separately in a waterfall plot.

Descriptive statistics according to the individual scoring will be provided for EuroQol (EQ-5D) and EORTC (QLQ-C30) by cycle and at the end of treatment for each treatment arm separately; additional modeling might be performed.

An exploratory analysis that relates PFS to BOR-5 will be conducted for each treatment group separately. Subjects will be classified according to their BOR; five PFS Kaplan-Meier curves will be plotted for each category of BOR and examined for presence of trend across the categories. In addition, potential of the 5-category Ordinal Response at a landmark to predict the PFS beyond the landmark will be explored in the following way. Subjects who had not experienced PD by Week 12 will be classified into 4 categories according to their 5-category Ordinal Response at Week 12. Four overlaid Kaplan-Meier curves for PFS beyond Week 12 will be plotted and examined for presence of trend across the categories. Similar

exploratory analysis will be performed for 5-category Ordinal Response at later weeks, although diminishing size of the data set will lead to higher variability of Kaplan-Meier curves.

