6.3 Post-Treatment: Follow-Up

Trial Period:	Post-Treatment				
Visit	Safety Follow-Up ⁹	Follow-Up ¹⁰ Visit 1	Follow-Up ¹⁰ Visit 2	Follow-Up ¹⁰ ≥ Visit 3	Survival Follow-Up ¹ ≥ Visit 1
Time from Last Dose of Trial Treatment	30 Days	3 Months	6 Months	≥ 9 Months	Every 3 Months
Scheduling Window (Days)	± 3	± 7	± 7	± 7	± 30
Administrative Procedures					
Review Medications	X				
Subsequent Antineoplastic Therapy Status	X	X	X	X	X
Survival Status ¹	←----->				X
Clinical Procedures / Assessments					
Review Adverse Events ^{2,3}	X	X	X	X	
Vital Signs and Weight ⁴	X				
Directed Physical Examination ¹¹	X	X	X		
12-Lead Electrocardiogram (ECG)	X				
ECOG Performance Status	X				
Efficacy Measurements					
Tumor Imaging ⁵	X	X	X	X	
Laboratory Procedures / Assessments					
CBC with Differential ⁶	X				
Comprehensive Chemistry Panel ⁶	X				
Laboratory Procedures / Assessments					
Urinalysis	X				
PT/INR and aPTT ⁷	As clinically indicated				
T3, FT4 and TSH	X				

Other Analyses					
Patient Reported Outcomes (PRO)					
EuroQol EQ-5D ⁸	X				
EORTC QLQ-C30 ⁸	X				

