
1 Once a subject experiences disease progression, starts a new antineoplastic therapy, or continues off study on any combination of treatments received during the trial, the subject moves into the Survival Follow-up Phase and should be contacted by telephone every 3 months to assess for survival status and start of new antineoplastic therapy, if applicable. In addition, follow-up will be required at time of study completion if last follow-up was >30 days prior. Updated survival status may be requested by the Sponsor at any time during the course of the study. Upon Sponsor notification, all participants who do not/will not have a scheduled study visit or study contact during the Sponsor defined time period will be contacted for their survival status (excluding participants who have a death event previously recorded), as per Section 7.1.5.
 
2 Record all AEs occurring within 30 days after the last dose of trial treatment. Report all SAEs (related and unrelated to trial treatment), ECIs, and irAEs occurring within 90 days of the last dose of trial treatment or until the start of new anti-cancer treatment, whichever comes first. After this time, report only SAEs and ECIs that are considered related to trial treatment.
 
3 Evaluate subjects for symptoms or clinical signs of non-cutaneous, new primary/recurrent malignancies before initiation of treatment, periodically during treatment, or as clinically indicated. Following discontinuation of dabrafenib, monitoring for non-cutaneous secondary/recurrent malignancies should continue for up to 6 months or until initiation of another anti-neoplastic therapy. Abnormal findings should be managed according to clinical practices.
 
4 Vital signs to include temperature, pulse, respiratory rate and blood pressure.
 
5 The same imaging technique should be used in a subject as was used earlier in the trial. Subjects who discontinue study treatment due to reasons other than disease progression, should continue to be assessed every 3 months by radiologic imaging. Monitoring should continue until the start of a new antineoplastic therapy, documented disease progression, or death, whichever occurs first.
 
6 See Section 7.1.3 for details regarding laboratory tests.
 
7 Coagulation factors (PT/INR and aPTT) should be determined throughout the study when clinically indicated.
 
8 PROs apply to Part 3 Post-Treatment subjects only: Patient reported outcomes (PROs) are to be administered by trained site personnel and completed electronically by subjects prior to all other study procedures in the following order: EuroQol EQ-5D first, followed by EORTC QLQ C-30. Subjects that complete 24 months on trial and opt to continue Dabrafenib and Trametinib will not be required to complete PROs at the 30-Day Safety follow up visit (Flow Chart 6.2). Subjects who complete 24 months on trial and move to Follow-Up or Survival Follow-Up will complete ePROs at the 30-Day Safety Follow-Up visit.
 
pembrolizumab. PROs do not apply to Part 1, Part 2, Part 4, or Part 5. It is most relevant and strongly recommended that ePROs are administered prior to drug administration, adverse event evaluation and disease status notification.
 
9 The mandatory Safety Follow-Up Visit should be conducted approximately 30 days after the last dose of trial treatment or before the initiation of a new antineoplastic treatment, whichever comes first. Subjects with an AE of Grade >1 will be further followed until the resolution of the AE to Grade 0-1 or until beginning of a new antineoplastic therapy, whichever occurs first.
 
10 Subjects who discontinue trial treatment for a reason other than disease progression will move into the Follow-up Phase and should be assessed every 3 months by radiologic imaging to monitor disease status. Follow-up Visit 1 should be scheduled 3 months after the last dose of trial treatment. Follow-up Visit 2 should occur 6 months after the last dose of trial treatment. After Follow-up Visit 3 subjects only need to be assessed every 3 months by radiologic imaging to monitor disease status, development of drug related SAEs and ECIs, and initiation of new antineoplastic therapy. Unless otherwise noted in the flow chart, every effort should be made to collect subject information until the start of new antineoplastic therapy, disease progression, or death, whichever occurs first.
 
11 Dermatological examination will be part of directed physical examination as indicated.
					

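### Table 41 makes primary PFS censoring of subjects who switch therapy before progression depend on whether PD or death follows; the effect on the treatment comparison cannot be sized from the documents

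*Combined protocol and SAP*

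**What the plan says.** Sections 8.1.3.1 and 8.2.3.1.1 define PFS as time to progression or death. Section 8.2.3.1.1 censors everyone else at the last disease assessment and has no rule for new therapy.

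Section 8.2.5.1 adds one, only for subjects without documented PD or death: "if they started new anti-cancer treatment, at the last disease assessment before initiation of the new anticancer treatment". It cites Table 40 for this, but Table 40 gives only censoring at the last assessment. Table 41 repeats the rule in row 2, headed "No PD and no death; new anticancer treatment is initiated". Rows 3 and 4 cover PD or death after at most one, and after two or more, missed assessments. In the primary analysis both read "Progressed at date of documented PD or death", with no condition on earlier new therapy.

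Sensitivity Analysis 1 differs from the primary only in row 4: "Censored at last disease assessment prior to the ≥ 2 missed disease assessment". Sensitivity Analysis 2 has "Progressed at date of new anticancer treatment" in row 2 but leaves rows 3 and 4 as in the primary.

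On follow-up, Section 6.3 footnote 1 says that once new therapy starts "the subject moves into the Survival Follow-up Phase and should be contacted by telephone every 3 months to assess for survival status". Footnote 5 limits imaging: "Monitoring should continue until the start of a new antineoplastic therapy, documented disease progression, or death, whichever occurs first". The same flow chart records "Subsequent Antineoplastic Therapy Status" at every post-treatment visit. Section 5.8.1 also ends disease follow-up at new therapy. Section 2.1 instead asks that subjects who stop treatment for reasons other than progression be assessed until progression is documented.

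**The concern.** Take two subjects in one arm who start new therapy on the same day, neither having progressed. The one still alive and event-free at cut-off is taken out of the risk set back at the last scan before the switch. The one who dies later stays at risk until the death and counts as an event. The only difference between them is what happened after the switch.

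The log-rank test, the Cox model and the Kaplan-Meier estimates all assume that leaving the risk set does not use later outcomes. The rule governs the primary Part 3 test and hazard ratio, the median PFS, and the 44- and 74-week PFS estimates planned in Section 8.2.5.1. The plan can produce such cases, because deaths are still collected after the switch.

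**Working it through.** **1. The plan's own figure.** Inputs from Section 8.2.7: 60 per arm, medians 10 and 20 months (HR 0.5), 6-month accrual, 24 months in total, 5% yearly dropout. Hazards: λ = ln 2/10 = 0.0693 and ln 2/20 = 0.0347 per month; dropout η = −ln(0.95)/12 = 0.0043. The probability of an event is λ/(λ+η) × {1 − [e^(−18(λ+η)) − e^(−24(λ+η))]/[6(λ+η)]}, which gives 0.739 and 0.496. Events: 60 × 0.739 + 60 × 0.496 ≈ 74.1, against the stated 74. Power by Freedman's formula: √74 × (0.5/1.5) − 1.960 = 0.907, or 81.8%, against the stated 80%. The design reproduces, so it is the base for what follows.

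**2. Direction within an arm.** Let D be the events and T the time at risk when every switcher is followed to cut-off. Table 41 keeps D. It removes R, the time from the last pre-switch scan to end of follow-up for switchers with no later event. The ratio of event rates is [D/(T − R)]/[D/T] = T/(T − R) ≥ 1. It equals 1 only if no event-free switcher is removed while others remain at risk.

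**3. Size within an arm.** The documents give no switch rates, so all rates here are assumptions. With switching at 2-8 months, unrelated to prognosis and with the hazard unchanged afterwards:
- 10% switching: event rate +5% (true median 10 months) to +7% (20 months).
- 25% switching, true median 10: +14-15%; estimated median 9.2; 44-week PFS 46% against 50%.
- 25% switching, true median 20: +19-20%; estimated median 16.6-16.7; 74-week PFS 49% against 55%.

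A second model, with a constant switching rate and a 10-month median, gives ratios of 1.02, 1.04, 1.09 and 1.17 at 5%, 10%, 18% and 32% switched. Letting the post-switch hazard run from 0.1 to 2 times the earlier one widens the range to 1.01-1.49.

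**4. Between arms, same assumptions as the first model** (HR, then power or one-sided type I error; standard error about 0.7 points for power and 0.1-0.2 for type I error):

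| True HR | Switching, control/triplet | As written | Censor all at switch | Count all to cut-off |
|---|---|---|---|---|
| 0.50 | 10%/25% | 0.56, 69% | 0.51, 76% | 0.50, 84% |
| 0.50 | 5%/15% | 0.54, 75% | 0.50, 79% | 0.50, 84% |
| 1 | 25%/10% | 0.92, 6.5% | 0.985, 3.1% | 1.00, 2.6% |
| 1 | 15%/5% | 0.95, 4.7% | 0.99, 3.0% | 1.00, 2.5% |
| 0.50 or 1 | 10%/10% | 0.50 or 1.00 | 0.50 or 1.00 | 0.50 or 1.00 |

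If only deaths are seen after the switch (median 12-20 months), true HR 0.50 at 10%/25% becomes 0.57-0.60 as written, 0.51 with all censored and 0.53-0.57 with all counted. Only part of the gap between the first two comes from the dependence on later outcome: 0.032/0.094 = 34% at a 12-month death median and 0.042/0.067 = 63% at 20 months. The rest is the assumed death hazard.

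**5. Switching related to prognosis.** One arm, true median 10, 25% switching. Half the subjects have three times the hazard and are four times as likely to switch; only deaths are seen afterwards (median 20 months). As written, the median is 10.2 against 10.0, and 44-week PFS is 50.2-50.4% against 49.6-49.8%. At 74 weeks the truth is 33.1%; the written rule gives 32.8%, censoring all gives 36.9% and counting all gives 41.0%.

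**6. Sensitivity analyses.** Sensitivity Analysis 2 dates the event at the switch for a switcher with no later event, but at the later event for one who has it, so it depends on later outcome too. Sensitivity Analysis 1 acts only if scans that are no longer required count as missed, which is undefined; even then an event after at most one missed scan stays. With true HR 0.50 at 10%/25% it gives 0.52-0.53 if 6-weekly scans count as missed, 0.54-0.57 if 3-monthly scans do, and 0.56-0.60 if none do.

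**The case against.** The reading of Table 41 is hard to dispute; what it implies is open to challenge. A reader might infer that the rule makes PFS look too short in any arm with switching. The documents do not support that. The certain direction in step 2 is against following all switchers, and if imaging stops at the switch that comparison sees only deaths, so it is not true PFS either. Step 5 shows the written rule slightly high on the median and nearer the truth than both alternatives. This objection stands.

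It is also fair that every size rests on assumed switch rates, that equal switching leaves the hazard ratio almost untouched, and that 25% against 10% is a strong contrast. Counting post-switch deaths agrees with the PFS definition and the ITT population (Section 8.2.4.1); row 2 is the part that departs from it. Making censoring at the switch the single primary rule would therefore be partly a matter of choice.

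Finally, Part 3 has been analysed without a significant PFS gain (Section 5.2.5), so no false positive arose, and an amendment cannot restore pre-specification. None of this makes a censoring rule that uses later outcomes coherent. It bears on the remedy and on how strongly the effect is described.

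**Conclusion.** The concern holds as an inconsistency in the primary endpoint rule that should be fixed. That censoring depends on later outcomes follows from the text alone. The higher within-arm event rate is certain only relative to following all switchers and counting every PD or death. The sizes in step 3 also need switching unrelated to prognosis and a hazard unchanged by it.

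Between arms, neither size nor direction can be stated for this trial. More switching in control would favour the triplet; more in the triplet arm would cost power.

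A reader might go further and infer that the rule hid a benefit, since Section 5.2.5 reports more discontinuations for adverse events in the experimental arm. That does not follow. A discontinuation is not a switch, Section 5.6.1.1.2 lets subjects who stop one drug continue the others, and no switch counts are given.

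**What to change.** Treat every subject who starts new therapy before documented PD the same way, whatever follows:

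- **(a)** Count PD or death regardless of new therapy and drop the backdating in row 2. This fits Sections 8.1.3.1 and 8.2.3.1.1. Event-free switchers must also be carried forward past the switch: if imaging ends there, the last assessment is already the last pre-switch scan, and deleting row 2 alone changes nothing.
- **(b)** Censor every pre-PD switcher at the last assessment before new therapy, and limit rows 3 and 4 to events without earlier new therapy.

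Name one as primary and report the other beside it. Align Section 8.2.3.1.1, the text of Section 8.2.5.1, Table 40 and Table 41. Give Sensitivity Analysis 2 a single row for all switchers, and state whether scans after a switch count as missed. Reconcile Section 2.1 with Sections 5.8.1 and 6.3 on imaging after new therapy. Report by arm the number of pre-PD switchers and their later PD or deaths, and label the result a re-analysis.

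Costs: an amendment under Section 8.2. Option (b) needs no new data, since subsequent therapy and survival are recorded, but it turns about 5-14 events, against 74 planned, into censored times. Option (a) may see only deaths after the switch. Both can be biased if switching is related to prognosis: at true HR 1 with 10%/25% switching and half the subjects at 2-3 times the hazard, (b) gives 0.96-0.98 and (a), seeing deaths only, gives 0.90-0.96. The aligned Sensitivity Analysis 2 moves further from a true 0.50 (0.73 against 0.68-0.70 at 10%/25%), because it scores the switch itself as progression.
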